**Study Design:**

Patients with a recent ACS and/or undergoing PCI with NVAF and planned treatment with P2Y12 inhibitor and oral anticoagulation for at least 6 months will be evaluated for eligibility during their ACS or post-PCI hospitalization. Randomization can be performed up to 14 days after the ACS or PCI and should take place as early as possible after cessation of parenteral anticoagulant and when clinically stable. Both patients with and without prior oral anticoagulant treatment can be included in this trial. Patients who are on a VKA prior to randomization will have VKA discontinued and will not be dosed with apixaban until the INR is less than 2.0. At the time of enrollment, each patient who meets inclusion / exclusion criteria will be randomized via IVRS using a 2 x 2 factorial design to either apixaban or VKA and to either aspirin or aspirin placebo. Randomization will be stratified by indication at enrollment (ACS vs. PCI).

Overall, the trial will include approximately 1/3 of patients with a recent ACS.

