#### **3.1 Study Design and Duration**

Patients with a recent ACS and/or undergoing PCI for another indication with either active or a history of NVAf and planned treatment with P2Y12 agent and oral anticoagulation for at least six months will ideally be evaluated for eligibility during their ACS or PCI hospitalization. Randomization can be performed up to 14 days after the ACS or PCI and should take place as early as possible after cessation of parenteral anticoagulant and when clinically stable. Both patients with and without prior VKA treatment can be included in this trial. Patients who are on a VKA prior to randomization will have VKA discontinued and will not be dosed with apixaban until the INR is less than 2.0. (Please refer to your country's approved label language for apixaban and VKA.) At the time of enrollment, each patient who meets inclusion/exclusion criteria will be randomized via IVRS using a 2 x 2 factorial design to either apixaban or VKA and to either aspirin or aspirin placebo. Randomization will be stratified by indication at enrollment (ACS vs PCI). Overall, the trial will include approximately 1/3 of patients with a recent ACS.

Approximately 690 sites will participate in this study, which will be conducted globally, including participation of countries located in North America, Europe, Asia and Latin America.

The study design schematic is presented in [Figure 3.1-1](#).

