#### 4.5 Selection and Timing of Dose for Each Subject

Subjects randomized to apixaban will be dosed at 5 mg bid, unless they meet at least two of the following criteria for dose reduction to 2.5 mg BID:

- Age  $\geq$  80 years
- Weight  $\leq$  60 kg
- Serum creatinine  $\geq$  1.5 mg/dL (133 micromol/L)

Subjects randomized to apixaban may have their dosages increased or decreased during the 6 month treatment period if at least two of the three above criteria change during the study.

Subjects randomized to VKA should be titrated up for an INR target goal of 2.0 to 3.0. Dosages of VKA to achieve that range should be per local standards of care and per investigator clinical judgment.

Both the oral anticoagulant (apixaban or VKA) and the antiplatelet agents (blinded aspirin once daily or blinded placebo once daily) must be started within 24 hours of randomization.

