## 5 STUDY ASSESSMENTS AND PROCEDURES

### 5.1 Flow Chart/Time and Events Schedule

**Table 5.1-1: Baseline and Randomization (CV185316)**

Procedure	Screening/ Randomization Visit	Notes
Eligibility Assessments		
Informed Consent	X	
Inclusion/Exclusion Criteria	X	
Medical History	X	Include assessment of alcohol use, tobacco use, prior VKA use, and CHADS-VASC and HAS-BLED scores
Safety Assessments		
Physical Examination	See Notes	Only if deemed necessary by treating physician. Results of examination will be documented in patient's chart, not on CRF
Vital Signs	X	Blood Pressure and Weight
Assessment of Signs and Symptoms	See Notes	Only if deemed necessary by treating physician. Results of assessment will be documented in patient's chart, not on CRF
Serious Adverse Events Assessment	See Notes	Refer to section 6.1 of the protocol for SAE definitions applying to this study.
Adverse Events Assessment	N/A	
Laboratory Tests	X	Local lab: CBC, chemistry(CHEM7 or equivalent for determination of serum creatinine), coagulation (for PT/PTT/INR) (local lab within 7 days can be used)
Urine Pregnancy Test* ( WOCBP only )	X	*If applicable Serum pregnancy test to be performed only if urine test is positive or un-interpretable
Study Drug		
Randomize	X	
Dispense Study Drug (administer within 24 hours of randomization)	X	Those supplied by BMS or sourced by the investigator

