**Table 5.1-2: Short-term Procedural Outline (CV185316)**

Procedure (± 7 days is allowed)	Visit 1 a (1 month b )	Visit 2 a (3 months b )	Visit 3 a (6 months b )	Phone visits (at 2, 4, and 5 months b )	Phone or In-Person Follow-up (30 day +/- 7 days after End of Treatment)	Notes
Safety Assessments						
Targeted Physical Examination	X	X	X			Only if deemed necessary by treating physician
Vital Signs	X	X	X			Blood pressure and weight
Assessment of Signs and Symptoms	X	X	X		X (if in-person visit)	
Serious Adverse Event Assessment	X	X	X	X	X	Refer to section 6.1 of the protocol for SAE definitions applying to this study.
Targeted Adverse Events Assessment	X	X	X	X	X	See section 6.2
Laboratory Tests	INR for VKA	INR for VKA	INR for VKA	INR for VKA	INR for VKA	To be performed locally for VKA subjects
Urine Pregnancy Test* ( WOCBP only )	X	X	X	X	X	*If applicable Serum pregnancy test to be performed only if urine test is positive or un-interpretable
Bleeding Assessment	CBC, if applicable	CBC, if applicable	CBC, if applicable	CBC, if applicable	CBC, if applicable	To be performed locally
Efficacy Assessments						
Death/Ischemic Events Assessment	Diagnostic studies, if applicable	Diagnostic studies, if applicable	Diagnostic studies, if applicable	Diagnostic studies, if applicable	Diagnostic studies, if applicable	To be performed locally

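### Protocol 4.5 sets a 24-hour apixaban start with no exception for the protocol's own INR hold, and its in-study dose sentence counts criteria that change instead of criteria met

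*Protocol*

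**What the plan says.** **Start of treatment.** Protocol 4.5 names apixaban and VKA together with the blinded aspirin or placebo and says they "must be started within 24 hours of randomization". The schedule in Table 5.1-1 repeats it: "Dispense Study Drug (administer within 24 hours of randomization". Neither place gives an exception.

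The synopsis (Study Design) says that patients on a VKA before randomization "will have VKA discontinued and will not be dosed with apixaban until the INR is less than 2.0". Protocol 3.1 repeats that they "will not be dosed with apixaban until the INR is less than 2.0" and refers sites to local labels. SAP 2.1 describes the same hold but adds a 4-day alternative.

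**Dose.** The first dose sentence in Protocol 4.5 gives 5 mg BID "unless they meet at least two of the following criteria for dose reduction to 2.5 mg BID". The criteria are age 80 or over, weight 60 kg or less, and serum creatinine 1.5 mg/dL or more. The in-study sentence then says the dose may go up or down "if at least two of the three above criteria change during the study".

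**The concern.** The two start rules bind the same subjects and neither refers to the other. Where they collide, the site must either miss a stated deadline or breach a stated safety hold. The unsafe error is apixaban given while the INR is still therapeutic, in a patient who is also on a P2Y12 inhibitor and possibly aspirin, in a trial whose primary endpoint is bleeding.

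The two dose sentences count different things. The first asks how many criteria are met now, and the second asks how many have changed. A subject can go from one criterion met to two through a single change. In that case the sentence written for in-study adjustment is not triggered, although the first sentence points to the lower dose.

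**Working it through.** The plan gives no figure on either point, so there is nothing to reproduce. The start rule is checked by setting the texts side by side, and the dose rule by enumeration.

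**1. Can a subject reach 24 hours with an INR of 2.0 or more?**

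- Prior-VKA patients are eligible (Protocol 3.1).
- No inclusion or exclusion criterion in Protocol 3.3.1 or 3.3.2 caps the INR.
- The baseline coagulation result may be several days old: "coagulation (for PT/PTT/INR) (local lab within 7 days can be used" (Table 5.1-1).
- Randomization is to happen as early as possible once parenteral anticoagulation has stopped and the patient is stable (Protocol 3.1). An INR below 2.0 is not a condition.
- Table 5.1-2 schedules later INRs for VKA subjects only, so no scheduled test releases the hold in the apixaban arm.

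The text therefore does not prevent the collision. It arises only for a subject who was on a VKA, is assigned to apixaban, and still has an INR of 2.0 or more 24 hours after randomization. The only hold length in the documents is the 4 days in SAP 2.1, which is 4 × 24 = 96 hours against a limit of 24. That is descriptive wording, not an estimate of how long holds last.

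**2. What does the in-study dose sentence cover?**

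Treat each of the three criteria as met or not met, which gives 2³ = 8 states. Ordered changes between different states number 8 × 7 = 56. Age cannot move from met to unmet, which removes 4 × 4 = 16 and leaves 40. A change crosses the threshold if the number of criteria met moves from below two to two or more, or the reverse. The in-study sentence is triggered if two or more criteria change.

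| Criteria changing | Possible changes | Cross threshold | Do not cross | Sentence triggered? |
|---|---|---|---|---|
| 1 | 20 | 10 | 10 | No |
| 2 | 16 | 8 | 8 | Yes |
| 3 | 4 | 4 | 0 | Yes |
| Total | 40 | 22 | 18 | 20 |

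- Crossings not covered: 22 − (8 + 4) = 10, all single-criterion. Six move toward 2.5 mg and four toward 5 mg. By criterion, 2 are age, 4 weight and 4 creatinine.
- Triggers without a crossing: 8, all two-criterion swaps.
- Total disagreement between the two ways of counting: 10 + 8 = 18 of 40.

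*Not covered.* An 82-year-old with creatinine 1.2 mg/dL falls from 62 to 59 kg. One criterion was met and now two are, after one change. Sites would see this, because Table 5.1-2 schedules "Blood pressure and weight" at Visits 1 to 3. Creatinine has no scheduled follow-up in that table.

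*Triggered without need.* In a subject under 80, weight rises above 60 kg while creatinine rises to 1.5 mg/dL or more. Two criteria have changed, but one was met before and one is met after.

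**The case against.** **On the start rule.** The INR hold is a specific prohibition for a defined subgroup, while the 24-hour rule is general, so a careful site would follow the hold. Protocol 3.1 also points to local labels. A site can avoid the conflict by delaying randomization, which is allowed up to 14 days after the event. All of this shows that a safe reading exists. None of it waives the deadline in 4.5 or Table 5.1-1, and the protocol does not tell sites to delay randomization until the INR is below 2.0.

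**On the dose rule.** A reader might infer that the protocol orders a wrong dose. It does not. The in-study sentence is permissive and forbids nothing. The first sentence is mandatory, is not limited to baseline, and gives 2.5 mg to the 82-year-old above. The footnote to SAP Table 7.6.1.3 also speaks of VKA subjects who meet the dose-adjustment criteria, which supports criteria met as the intended rule. This objection stands: the defect is a misstated sentence, not two conflicting orders. The enumeration also weights every logical change equally, so it says nothing about how often patients are affected.

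**On the analysis.** A reader might infer that the start conflict biases the primary comparison. The documents do not support that. Bleeding time runs from first dose (SAP 4.1), and a late start is not among the relevant deviations in SAP 7.2, so it removes no one from the Evaluable Population. Any shift in the clock comes from the INR hold itself and would remain after the wording is corrected.

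A reader might also infer that SAP 7.6.1.2 breaks a promise, because it runs the randomized-subjects sensitivity analysis only during the treatment period. It does not. Protocol 8.4.3.1 promises that analysis on the intention-to-treat population, and Protocol 8.4.3 and 8.4.3.1 place the bleeding endpoint within a treatment period that starts at first dose.

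**Conclusion.** Both wording faults are real and should be corrected. For an apixaban subject coming off a VKA with an INR still at 2.0 or more at 24 hours, the protocol gives two instructions that cannot both be followed. The in-study dose sentence leaves 10 of 22 threshold crossings uncovered and permits a dose change in 8 of 18 non-crossings. That count assumes only that each criterion is met or not met and that age cannot fall.

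The number of subjects affected by either fault is not in the documents. The case rests on patient safety and on instructions that sites can carry out. It does not rest on bias, and no power, alpha or endpoint definition changes.

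A lesser observation is that the sensitivity analysis in SAP 7.6.1.2 nearly repeats the primary analysis and cannot count bleeds before the first anticoagulant dose. That is a limit on its usefulness.

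**What to change.** **Protocol 4.5 and Table 5.1-1.** Word the start rule as: *within 24 hours of randomization, or, for apixaban subjects previously on a VKA, as soon as INR is below 2.0*.

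**Protocol 4.5, in-study dose.** Replace the sentence with: *2.5 mg BID whenever at least two of the three criteria are currently met, 5 mg BID otherwise*.

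**SAP 2.1.** Align the 4-day wording with the protocol if the SAP is revised; this is cosmetic.

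**Optional, SAP 7.6.1.2.** Keep the current analysis and add a supportive one from randomization over the Intended Treatment Period. State that it includes off-drug time, which can dilute a true difference and so favours non-inferiority. As an illustration, assume 10% to 30% of follow-up is off drug at HR 1 and take a weighted average. An on-drug HR of 1.2 then appears as 0.9 × 1.2 + 0.1 × 1 = 1.18 at 10%, and 0.7 × 1.2 + 0.3 × 1 = 1.14 at 30%. For that reason it should not replace the on-treatment analysis.

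**Cost.** The two protocol edits need an amendment with IRB/IEC approval (Protocol 9.1.1) across about 690 sites (Protocol 3.1). SAP 7.9 reports the review at 50% completion as already done, so the edits reach only subjects still on treatment or yet to enrol. The optional analysis needs only a SAP revision and no new data, because bleeding is recorded at each visit (Protocol 3.1) and subjects who stop drug are still followed (Protocol 3.6).

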#### 4.6 Blinding/Unblinding

Apixaban or VKA will be open-label. This section will not apply to those agents.

Aspirin (or matching placebo) will be double blinded. Requests for emergency unblinding for patient, only, should be made by the investigator(s) to the designated regional medical monitor or, if that person cannot be contacted, to the global medical monitor.

#### 4.7 Treatment Compliance

Drug compliance for apixaban and aspirin/aspirin placebo will be defined as between 80% to 120%. Pill counts, guided by patient-completed drug diaries, will assist completion of the appropriate eCRF pages, but actual determination of compliance will be determined by the Sponsors. Diary cards must be distributed to subjects, but completion of the cards is at the discretion of the subjects.

#### 4.8 Destruction or Return of Investigational Product

For this study, IP (those supplied by BMS, a vendor, or sourced by the investigator) such as partially used study drug containers may be destroyed on site.

If...	Then...
IP supplied by BMS (including its vendors)	
Any unused IP supplied by BMS can only be destroyed after being inspected and reconciled by the responsible Study Monitor unless IP containers must be immediately destroyed as required for safety, or to meet local regulations (eg, cytotoxics or biologics).
 
If IP will be returned, the return will be arranged by the responsible Study Monitor.

If...	Then...
IP sourced by site, not supplied by BMS (or its vendors) (examples include IP sourced from the sites stock or commercial supply, or a specialty pharmacy)	It is the investigator's or designee's responsibility to dispose of all containers according to the institutional guidelines and procedures.

It is the investigator's or designee's responsibility to arrange for disposal, provided that procedures for proper disposal have been established according to applicable federal, state, local, and institutional guidelines and procedures, and provided that appropriate records of disposal are kept.

The following minimal standards must be met:

- On-site disposal practices must not expose humans to risks from the drug
- On-site disposal practices and procedures are in agreement with applicable laws and regulations, including any special requirements for controlled or hazardous substances
- Written procedures for on-site disposal are available and followed. The procedures must be filed with the site's SOPs and a copy provided to BMS upon request
- Records are maintained that allow for traceability of each container, including the date disposed of, quantity disposed, and identification of the person disposing the containers. The method of disposal, ie, incinerator, licensed sanitary landfill, or licensed waste disposal vendor must be documented
- Accountability and disposal records are complete, up-to-date, and available for the Monitor to review throughout the clinical trial period

It is the investigator's or designee's responsibility to arrange for disposal of all empty containers.

If conditions for destruction cannot be met the responsible Study Monitor will make arrangements for return of IP provided by BMS (or its vendors). Destruction of non-IP sourced by the site, not supplied by BMS, is solely the responsibility of the investigator or designee.

For this study, IP (those supplied by BMS or its vendors such as full or partially used study drug containers, vials, syringes) cannot be destroyed on-site. It is, however, the investigator's or designee's responsibility to arrange for disposal of all empty IP containers, provided that procedures for proper disposal have been established according to applicable federal, state, local, and institutional guidelines and procedures, and provided that appropriate records of disposal are kept. The return of full or partially used IP supplied by BMS or its vendors will be arranged by the responsible Study Monitor.

For subjects where the IP is not directly supplied by BMS (e.g., commercially-sourced apixaban or VKA dispensed from a pharmacy by a physician's prescription), leftover medication after the 6 month treatment period does not need to be returned to the site.

For subjects where the IP is directly supplied by BMS or one of its vendors, the site obligation is to request the subject to return the medication to the site; it is the subject responsibility, not the site's, to comply.

Please refer to [Section 9.2.2](#) for additional guidance on IP records and documentation.

#### **4.9 Retained Samples for Bioavailability / Bioequivalence**

Not Applicable.

## 5 STUDY ASSESSMENTS AND PROCEDURES

### 5.1 Flow Chart/Time and Events Schedule

**Table 5.1-1: Baseline and Randomization (CV185316)**

Procedure	Screening/ Randomization Visit	Notes
Eligibility Assessments		
Informed Consent	X	
Inclusion/Exclusion Criteria	X	
Medical History	X	Include assessment of alcohol use, tobacco use, prior VKA use, and CHADS-VASC and HAS-BLED scores
Safety Assessments		
Physical Examination	See Notes	Only if deemed necessary by treating physician. Results of examination will be documented in patient's chart, not on CRF
Vital Signs	X	Blood Pressure and Weight
Assessment of Signs and Symptoms	See Notes	Only if deemed necessary by treating physician. Results of assessment will be documented in patient's chart, not on CRF
Serious Adverse Events Assessment	See Notes	Refer to section 6.1 of the protocol for SAE definitions applying to this study.
Adverse Events Assessment	N/A	
Laboratory Tests	X	Local lab: CBC, chemistry(CHEM7 or equivalent for determination of serum creatinine), coagulation (for PT/PTT/INR) (local lab within 7 days can be used)
Urine Pregnancy Test* ( WOCBP only )	X	*If applicable Serum pregnancy test to be performed only if urine test is positive or un-interpretable
Study Drug		
Randomize	X	
Dispense Study Drug (administer within 24 hours of randomization)	X	Those supplied by BMS or sourced by the investigator

**Table 5.1-2: Short-term Procedural Outline (CV185316)**

Procedure (± 7 days is allowed)	Visit 1 a (1 month b )	Visit 2 a (3 months b )	Visit 3 a (6 months b )	Phone visits (at 2, 4, and 5 months b )	Phone or In-Person Follow-up (30 day +/- 7 days after End of Treatment)	Notes
Safety Assessments						
Targeted Physical Examination	X	X	X			Only if deemed necessary by treating physician
Vital Signs	X	X	X			Blood pressure and weight
Assessment of Signs and Symptoms	X	X	X		X (if in-person visit)	
Serious Adverse Event Assessment	X	X	X	X	X	Refer to section 6.1 of the protocol for SAE definitions applying to this study.
Targeted Adverse Events Assessment	X	X	X	X	X	See section 6.2
Laboratory Tests	INR for VKA	INR for VKA	INR for VKA	INR for VKA	INR for VKA	To be performed locally for VKA subjects
Urine Pregnancy Test* ( WOCBP only )	X	X	X	X	X	*If applicable Serum pregnancy test to be performed only if urine test is positive or un-interpretable
Bleeding Assessment	CBC, if applicable	CBC, if applicable	CBC, if applicable	CBC, if applicable	CBC, if applicable	To be performed locally
Efficacy Assessments						
Death/Ischemic Events Assessment	Diagnostic studies, if applicable	Diagnostic studies, if applicable	Diagnostic studies, if applicable	Diagnostic studies, if applicable	Diagnostic studies, if applicable	To be performed locally

**Table 5.1-2: Short-term Procedural Outline (CV185316)**

Procedure (± 7 days is allowed)	Visit 1a (1 month b )	Visit 2a (3 months b )	Visit 3a (6 months b )	Phone visits (at 2, 4, and 5 months b )	Phone or In-Person Follow-up (30 day +/- 7 days after End of Treatment)	Notes
Study Drug						
Dispense Study Drug	X	X				
Drug Compliance	X	X	X	X		At Follow-up Visit, assess transition to Oral Anticoagulant (OAC)

a For patients who decline further treatment but still permit follow up, visits 1, 2, and 3 may be performed by telephone

b 30 day months

### **5.1.1 Retesting During Screening Period**

Retesting of laboratory parameters and/or other assessments within any single Screening period will be permitted (in addition to any parameters that require a confirmatory value).

Any new result will override the previous result (ie, the most current result prior to Randomization) and is the value by which study inclusion will be assessed, as it represents the subject's most current, clinical state.

### **5.2 Study Materials**

- Urine pregnancy kits (for WOCBP only)
- Patient education materials and site support tools
- Patient reminder cards (optional) to be used for helping patients remember to take their study medications.

### **5.3 Safety Assessments**

No specific safety assessments other than the laboratory tests, clinical assessments of bleeding episodes, AEs/SAEs indicated in [Table 5.1-1](#) and [Table 5.1-2](#), are required.

#### **5.3.1 Imaging Assessment for the Study**

No radiological assessments are mandated.

### **5.4 Efficacy Assessments**

No specific efficacy assessments are mandated. Clinical judgment should be executed in evaluating what diagnostics and tests to order to assess the study's efficacy endpoints. These suspected endpoints should be documented in the appropriate sections of the electronic case report form.

